7.3.7.1. Progression-Free Survival by RECIST v1.1

Under RECIST v1.1, PFS is defined as the length of time between the baseline visit (Day 1) and the earlier of death or first assessment of PD as assessed by RECIST v1.1.

7.3.7.2. Progression-Free Survival by mRECIST

Under mRECIST, PFS is defined as the length of time between the baseline visit (Day 1) and the earlier of death or first confirmed assessment of PD (as described in [Table 6](#)).

7.3.8. Overall Survival

Overall survival is defined as the interval between Cycle 1 Day 1 and the date of death due to any cause. Date of death will be determined using the Death Report, the Survival Follow-Up, and the Subject Status CRFs. Subjects who are lost-to-follow-up or still alive at the time of analysis will be right-censored at the earlier of the date that the subject was last known alive and the clinical data cutoff date for the analysis. The last known alive date is defined as the later of the last study visit and the date the subject was last known alive from the Survival Follow-Up and Subject Status CRFs, and the analyses will be summarized for the FAS population.

Kaplan-Meier time to event curves will be presented by treatment groups. Median survival will be estimated using the Kaplan-Meier method. Kaplan-Meier estimates of 1-year and 2-year survival probabilities will be provided. Confidence intervals for median survival time will be calculated using the method of Brookmeyer and Crowley ([1982](#)).

[REDACTED]

8. SAFETY AND TOLERABILITY

Sample data displays are provided in a separate document.

8.1. General Considerations

Summary tables may be replaced with listings when appropriate. For instance, an AE frequency table may be replaced with a listing if it only contains a few unique PTs reported on relatively few subjects.

Unless otherwise stated, table summaries will be limited to TEAEs.

8.2. Adverse Events

8.2.1. Adverse Event Definitions

A TEAE is any AE either reported for the first time or worsening of a pre-existing event after first dose of study drug. For the subjects in the FAS population, analysis of AEs (as discussed below) will be limited to TEAEs, but data listings will include all AEs regardless of their timing in relation to study drug administration.

Adverse events will be tabulated by MedDRA PT and SOC. Severity of AEs will be graded using the National Cancer Institute CTCAE. The CTCAE version 4.03 is used for this study. The CTCAE reporting guidelines and grading details are available on the Cancer Therapy Evaluation Program website.

The subset of AEs considered by the investigator to be related to INCAGN01949, nivolumab, or ipilimumab will be considered to be treatment-related AEs and will be summarized. If the investigator does not specify the relationship of the AE to study drug, the AE will be considered to be treatment-related. The incidence of AEs and treatment-related AEs will be tabulated. In addition, SAEs will also be tabulated.

A grading (severity) scale is provided for each AE term. If the toxicity is not included in the CTCAE v4.03 criteria, it will be rated on a scale of 1 to 5 as follows: 1 = mild, 2 = moderate, 3 = severe, 4 = life-threatening, and 5 = death related to AE. All toxicities will be graded based on the worst level reached, not the level they may have reached if they had not been treated. When the intensity of an AE changes over time for a reporting period (eg, between visits), each

change in intensity will be collected as an AE until the event resolves. Only the worst grade will be reported in AE summaries. Also, the Grade 3 or higher AEs will be summarized.

Any missing onset date, causality, or severity must be queried for resolution. Unresolved missing causality and severity will be handled according to the following rules:

- An unresolved missing causality will be considered treatment-related.
- An unresolved missing severity will be identified as an unknown severity.

For purposes of analysis, all AEs will be considered TEAEs unless the AE can unequivocally be defined as not treatment-emergent.

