2. STUDY OBJECTIVES AND ENDPOINTS

2.1. Study Objectives

2.1.1. Primary Objectives

Phase 1

- To evaluate the safety, tolerability, and DLTs of INCAGN01949 in combination with immune therapies and to define the recommended dose(s) of INCAGN01949 when given in combination with immune therapies.

[figure not shown]
Phase 2

- To evaluate the efficacy of INCAGN01949 when given in combination with immune therapies by assessing ORR per RECIST v1.1.

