The occurrence of AEs should be sought by nondirective questioning of the subject during the screening process after signing the ICF and at each visit during the study. Adverse events may also be detected when they are volunteered by the subject during the screening process or between visits, or through physical examination, laboratory test, or other assessments. To the extent possible, each AE should be evaluated to determine:

- The severity grade (CTCAE Grade 1 to 5).
- Whether there is at least a reasonable possibility that the AE is related to the study treatment: suspected (yes) or not suspected (no).
 - ***Note: causality assessment for each agent administered per study must be indicated.***
- The start and end dates, unless unresolved at final follow-up.
- The action taken with regard to study drug.
- The event outcome (eg, not recovered/not resolved, recovered/resolved, recovering/resolving, recovered/resolved with sequelae, fatal, unknown).
- The seriousness, as per SAE definition provided in Section [8.3.1](#).

Unlike routine safety assessments, SAEs are monitored continuously and have special reporting requirements (see Section [8.3.2](#)).

All AEs should be treated appropriately. If an AE is treated with a concomitant medication or nondrug therapy, this action should be recorded on Adverse Event form and the treatment should be specified on the Prior/Concomitant Medications or Procedures and Non-Drug Therapy form in the eCRF.

Once an AE is detected, it should be followed until it has resolved or until it is judged to be permanent; assessment should be made at each visit (or more frequently if necessary) of any changes in severity, the suspected relationship to the study drug, the interventions required to treat the event, and the outcome.

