4. DATA HANDLING DEFINITIONS AND CONVENTIONS

4.1. Scheduled Study Evaluations and Study Periods

4.1.1. Day 1

Day 1 is the date that the first dose of study drug (INCAGN0 [REDACTED], nivolumab, or ipilimumab) is administered to the subjects.

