4.1.6. Cycle Length and Duration

Cycle 1 Day 1 is the day that the first dose of INCAGN01949, nivolumab, or ipilimumab is administered.

- **INCAGN01949:** For all treatment groups, INCAGN01949 will be administered IV over a 30-minute period on Day 1 of each Q2W (ie, 14-day) cycle.
- **Nivolumab:** In the doublet Treatment Groups A, C, F, G, and H, nivolumab will be administered IV per instructions provided in the package insert at a dose of 240 mg Q2W (eg, 14 days). In the triplet Treatment Groups D, E, J, K, and L, nivolumab will be administered IV per instructions provided in the package insert at a dose of 3 mg/kg Q2W (eg, 14 days). In the concurrent dosing Treatment Groups A, D, F, and J, nivolumab dosing will begin on Cycle 1 Day 1. In the sequenced/run-in dosing Treatment Groups C, E, G, H, K, and L, nivolumab dosing will begin on Cycle 3 Day 1.
- **Ipilimumab:** In Treatment Groups B, D, E J, K, and L, ipilimumab will be administered IV per instructions provided in the package insert to subjects at a dose of 1 mg/kg Q6W (eg, 42 days). In the concurrent dosing Treatment Groups B, D, and J, ipilimumab dosing will begin on Cycle 1 Day 1. In the sequenced dosing Treatment Groups E, K, and L, ipilimumab dosing will begin on Cycle 3 Day 1.

Subjects will continue to receive INCAGN01949, nivolumab, and ipilimumab as defined in the Protocol as long as the subject is deriving benefit and has not met any of the Protocol-defined conditions for treatment withdrawal.

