5.2. Treatment Groups

This is a Phase 1/2, open-label, nonrandomized, multicenter, dose-escalation study. The starting dose of INCAGN01949 is 70 mg, and up to 4 doses will be tested. Data will be summarized overall and by treatment group. Treatment group is defined as the dose regimen and dose schedule initially assigned.

Dose escalation of the triplet immune therapy combinations will begin enrolling once all of the applicable doublet combinations have cleared 3 INCAGN01949 dose levels (see [Table 1](#)) or the MTD or PAD of INCAGN01949 has been determined (whichever occurs first). The starting dose of INCAGN01949 will be 2 dose levels below the last dose cohort deemed safe in the doublet combination. The triplet immune therapy combinations will be explored in parallel.

- Treatment Group A
 - INCAGN01949 + 240 mg Q2W nivolumab
- Treatment Group B
 - INCAGN01949 + 1 mg/kg Q6W ipilimumab
- Treatment Group C
 - Run-in with INCAGN01949 × 2 doses followed by INCAGN01949 + 240 mg Q2W nivolumab
- Treatment Group D
 - INCAGN01949 + 3 mg/kg Q2W nivolumab + 1 mg/kg Q6W ipilimumab
- Treatment Group E
 - Run-in with INCAGN01949 × 2 doses followed by INCAGN01949 + 3 mg/kg Q2W nivolumab + 1 mg/kg Q6W ipilimumab

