3.2 Adverse Events				
3.2.1.1	Overall Summary of Treatment-Emergent Adverse Events – by Treatment Group and Dose	Phase 1 FAS Population	X	X
3.2.1.2	Overall Summary of Treatment-Emergent Adverse Events – by Treatment Group and Tumor Type	Phase 2 FAS Population	X	X
3.2.2.1	Summary of Treatment-Emergent Adverse Events by MedDRA System Organ Class and Preferred Term – by Treatment Group and Dose	Phase 1 FAS Population	X	
3.2.3.1	Summary of Treatment-Emergent Adverse Events by MedDRA System Organ Class and Preferred Term – by Treatment Group and Tumor Type	Phase 2 FAS Population	X	
3.2.4.1	Summary of Treatment-Emergent Adverse Events by MedDRA Preferred Term in Decreasing Order of Frequency – by Treatment Group and Dose	Phase 1 FAS Population	X	X
3.2.4.2	Summary of Treatment-Emergent Adverse Events by MedDRA Preferred Term in Decreasing Order of Frequency – by Treatment Group and Tumor Type	Phase 2 FAS Population	X	X
3.2.5.1	Summary of Treatment-Emergent Adverse Events by MedDRA System Organ Class, Preferred Term, and Maximum Severity – by Treatment Group and Dose	Phase 1 FAS Population	X	
3.2.5.2	Summary of Treatment-Emergent Adverse Events by MedDRA System Organ Class, Preferred Term, and Maximum Severity – by Treatment Group and Tumor Type	Phase 2 FAS Population	X	
3.2.6.1	Summary of Grade 3 or Higher Treatment-Emergent Adverse Events by MedDRA System Organ Class and Preferred Term – by Treatment Group and Dose	Phase 1 FAS Population	X	X
3.2.6.2	Summary of Grade 3 or Higher Treatment-Emergent Adverse Events by MedDRA System Organ Class and Preferred Term – by Treatment Group and Tumor Type	Phase 2 FAS Population	X	X
3.2.7.1	Summary of Any INCAGN01949 Treatment-Related Adverse Events by MedDRA System Organ Class and Preferred Term – by Treatment Group and Dose	Phase 1 FAS Population	X	X
3.2.7.2	Summary of Any INCAGN01949 Treatment-Related Adverse Events by MedDRA System Organ Class and Preferred Term – by Treatment Group and Tumor Type	Phase 2 FAS Population	X	X
3.2.8.1	Summary of Any Nivolumab Treatment-Related Adverse Events by MedDRA System Organ Class and Preferred Term – by Treatment Group and Dose	Phase 1 Nivolumab FAS Population	X	X

Table No.	Title	Population	Standard	In-Text
3.2.8.2	Summary of Any Nivolumab Treatment-Related Adverse Events by MedDRA System Organ Class and Preferred Term – by Treatment Group and Tumor Type	Phase 2 Nivolumab FAS Population	X	X

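### In run-in Groups C and E no planned adverse-event table separates the INCAGN01949-alone period from the combination period; a supplementary split would be a cheap improvement

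*SAP*

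**What the plan says.** SAP 8.2.1 defines treatment emergence with one clock: "A TEAE is any AE either reported for the first time or worsening of a pre-existing event after first dose of study drug". SAP 4.1.1 makes that clock start at the first dose of any of the three agents ("Day 1 is the date that the first dose of study drug" is given, with INCAGN01949, nivolumab and ipilimumab listed).

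SAP 5.2 describes Group C as "Run-in with INCAGN01949 × 2 doses followed by INCAGN01949 + 240 mg Q2W nivolumab". Group E has the same run-in followed by the triplet. On timing, SAP 4.1.6 says: "In the sequenced/run-in dosing Treatment Groups C, E, G, H, K, and L, nivolumab dosing will begin on Cycle 3 Day 1". Ipilimumab in Group E starts at the same visit.

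The FAS in SAP 5.3.1 needs one dose of any agent. The same section defines a nivolumab FAS and an ipilimumab FAS, each limited to subjects who received that agent. Appendix A lists Table 3.2.1.1, "Overall Summary of Treatment-Emergent Adverse Events – by Treatment Group and Dose", on the Phase 1 FAS, and the general TEAE, Grade 3 or higher, serious, immune-related and INCAGN01949-related tables follow the same pattern.

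On causality, Protocol 8.1.2 says "causality assessment for each agent administered per study must be indicated". SAP 8.2.1 requires missing values to be queried, and then: "An unresolved missing causality will be considered treatment-related".

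The Phase 1 primary objective (Protocol 2.1.1) begins: "To evaluate the safety, tolerability, and DLTs of INCAGN01949 in combination with immune therapies".

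**The concern.** In Groups C and E the single clock starts about four weeks before any checkpoint inhibitor is given. An event on Day 10 and an event on Day 60 therefore fall in the same column, although the first arose on INCAGN01949 alone. A subject who stops during the run-in stays in the denominator with no combination exposure.

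This matters because the question is about combination toxicity. Protocol 1.4 warns that INCAGN01949 may worsen immune-related events of the partner drugs, and Protocol 1.5.3 gives reasons to study both priming and concurrent dosing. A pooled column cannot show whether toxicity appeared before or after the partner drug was added. The protocol already treats the start of combination therapy as a meaningful origin, since PFS is counted from it (Protocol 2.2.2). The adverse-event plan has no counterpart.

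A second, smaller issue is agent-level attribution. Nothing in the SAP requires that an event attributed to nivolumab or ipilimumab begin on or after the first dose of that agent.

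**Working it through.** **Length of the run-in.** Cycles are 14 days (SAP 4.1.6). Cycle 3 Day 1 falls on Day 1 + 2 × 14 = 29, so nominal Days 1 to 28 are INCAGN01949 alone.

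**The plan's own figure.** Protocol 4.3.1 gives about 72 subjects for the safety expansion. With up to 6 subjects per dose (Protocol 4.1.2), 6 dose levels from 7 to 700 mg and 2 groups: 6 × 6 × 2 = 72, which reproduces it. With the SAP's 70 mg start there are 4 levels: 6 × 4 × 2 = 48. Enrollment stopped at 52 across Phase 1 (Protocol 9), and the split by group is not stated.

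**Which tables use which population (SAP Appendix A, Phase 1).**

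| Tables | Population |
|---|---|
| 3.2.1.1 overall, 3.2.6.1 Grade 3 or higher, 3.2.7.1 INCAGN01949-related, 3.2.16.1 serious, 3.2.25.1 and 3.2.27.1 immune-related | Phase 1 FAS |
| 3.2.8.1, 3.2.11.1, 3.2.14.1 nivolumab-related | Nivolumab FAS |
| 3.2.9.1, 3.2.12.1, 3.2.15.1 ipilimumab-related | Ipilimumab FAS |
| 3.2.22.1 nivolumab interruption, 3.2.23.1 ipilimumab interruption | Phase 1 FAS |

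The overall summary in SAP 8.2.4 also carries lines for events related to, or interrupting, nivolumab and ipilimumab. In Table 3.2.1.1 those lines are on the Phase 1 FAS. No listed adverse-event table is split at the first combination dose.

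**Whether subjects must reach Cycle 3.** The DLT period applies to Groups A, B and D only (Protocol 5.4.2). No visible replacement rule covers run-in drop-outs in C or E (Protocol 4.3.2, where one item is redacted).

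**Illustration of the denominator.** Assume one dose cohort of 6 with 2 subjects who have a combination-period event.
- One subject never reaches Cycle 3: 2/6 = 33.3% on the FAS, 2/5 = 40.0% among the exposed.
- Two never reach it: 2/6 = 33.3% against 2/4 = 50.0%.

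The documents give no run-in drop-out rate. For an assumed rate d, the chance that at least 1 of 6 is never exposed to the combination is 1 − (1 − d)^6: 26.5%, 46.9%, 73.8% and 88.2% for d = 5%, 10%, 20% and 30%.

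**Direction.** Let q be the run-in event rate, d the drop-out rate and p = 30% an assumed combination-period rate, all taken as independent. The pooled rate is q + (1 − q)(1 − d)p.
- q = 0, d = 10% to 30%: 27% to 21%, below p.
- q = 20%, d = 10% to 30%: 41.6% to 36.8%, above p.
- q = 10%, d = 20%: 0.10 + 0.90 × 0.80 × 0.30 = 31.6%, close to p.

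The pooled rate can therefore fall on either side of the combination-period rate.

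**Causality path.** Suppose a run-in event has no nivolumab causality recorded, the query stays unresolved, and the imputation is applied agent by agent. The event then becomes nivolumab-related. It enters Table 3.2.8.1 if the subject later received nivolumab, and the nivolumab line of Table 3.2.1.1 even if the subject never did. All three conditions are needed, and the SAP does not state the third.

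**The case against.** The strongest reply is that the run-in is part of the treatment. SAP 5.2 groups subjects by the regimen and schedule initially assigned, and C and E are defined as run-in followed by combination. Stopping during the run-in is an outcome of that regimen, so 2/6 is a proper regimen rate. The alternatives 2/5 and 2/4 condition on completing the run-in and drop anyone who left because of early toxicity. This stands, and it is why the overall column must stay. A reader might infer that the TEAE definition or the FAS denominator is wrong; the documents do not support that.

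The dedicated nivolumab- and ipilimumab-related tables already exclude subjects who never received the agent. That also stands and narrows the denominator point to the general tables, the agent-specific lines of Table 3.2.1.1, and Tables 3.2.22.1 and 3.2.23.1.

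A reader might also infer that the SAP will label run-in events as nivolumab-related. The text does not go that far. The protocol requires causality for each agent, missing values are queried first, and the rule says treatment-related without naming an agent. The CRF, which would settle what is recorded for an agent not yet given, is not available.

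The Part 2 enrollment rule at 40% concerns INCAGN01949-related events, and every C and E subject receives INCAGN01949 from Cycle 1, so its denominator is not in question. No formal comparison of C with A, or E with D, is planned (Protocol 4.2 and 9.3), so the point cannot rest on a biased comparison.

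Finally, Listings 2.6.1.1 to 2.6.1.3 and 2.6.2 would let a patient reader reconstruct the periods by hand. This is true at these sample sizes, but it leaves the summary tables silent on the question in the primary objective.

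**Conclusion.** This is a cheap improvement, not an error. The general Phase 1 tables describe the assigned regimen correctly. What is missing is any planned summary that separates nominal Days 1 to 28 from the combination period, in a study whose primary Phase 1 objective is safety in combination and for which only Phase 1 analyses will now be run.

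The actual size cannot be calculated, because neither the number of subjects in C and E nor the run-in drop-out is given. The figures of 33% against 40% or 50% are illustrations under assumed drop-out of one or two in six. It would be wrong to infer that the planned rates understate combination toxicity: under the scenarios above the pooled rate may be lower, higher or nearly equal. Labelling of run-in events as nivolumab- or ipilimumab-related is possible under the present wording, not certain.

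**What to change.** 1. Keep the as-assigned overall column. For Groups C and E, add a supplementary split of the key Phase 1 tables (overall, Grade 3 or higher, serious, immune-related, INCAGN01949-related):
   - *run-in*: before the first nivolumab or ipilimumab dose, Phase 1 FAS denominator;
   - *combination*: onset or worsening on or after that dose, with subjects who received it as denominator.

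   Footnote that the combination column is conditional on completing the run-in. Footnote also that onset date does not prove attribution: Protocol Table 1 gives mean INCAGN01949 half-lives of 140 to 264 hours, and Protocol 5.4.7 notes that immune-related events can appear months after the last dose.
2. Put the nivolumab and ipilimumab lines of Table 3.2.1.1, and Tables 3.2.22.1 and 3.2.23.1, on the matching agent FAS.
3. Add one sentence to SAP 8.2.1: imputation of missing causality for an agent applies only to events with onset on or after the first dose of that agent.

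The cost is SAP wording and a period flag. Event start dates, a new record at each change in severity (Protocol 8.1.2) and dosing by agent are already collected. The SAP is still its original version, based on Protocol Amendment 1, while the protocol is at Amendment 3, so this can go into a general update. The downside is small denominators in the combination-period columns, at most 6 per dose; SAP 8.1 already allows a listing in place of a sparse table.

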8.2.2. Dose-Limiting Toxicities

The number of subjects with DLTs and the type of DLT will be listed by dose level and treatment group. An AE for a subject will be identified as a DLT if the event is recorded as a Protocol-defined DLT on the AE CRF.

8.2.3. Adverse Events of Special Interest

8.2.3.1. Immune-Related Adverse Events

The number of subjects with irAEs and type of irAE will be listed by dose level and treatment group for the Phase 1 FAS population and by tumor type and treatment group in the Phase 2 FAS population. Adverse event terms will be reviewed periodically without respect to treatment group by the medical monitor and clinical scientist to determine which AE terms correspond to irAEs. This periodic review may also occur after database lock. The medical monitor and clinical scientist will also review investigator-reported irAEs to determine whether they qualify as irAEs. For example, a rash will be counted as an irAE even if the investigator did not report it as an irAE.

8.2.3.1.1. Adverse Events Identified as Incyte MedDRA Queries

Prospectively defined Incyte MedDRA Queries will be used to conduct analyses to evaluate the safety profile. Incyte MedDRA Queries are queries constructed by Incyte based on MedDRA PTs identified through review of standardized MedDRA queries for clinically relevant terms. Sets of included terms will be identified and archived before database lock for the individual studies. Incyte MedDRA Queries searches are to be conducted for the following TEAEs: hemorrhage events, dizziness, weight gain, thrombotic events, urinary tract infections, herpes zoster infections, tuberculosis, hepatitis B reactivation, and infections other than those stated previously. In addition, these other infections will be analyzed by subcategories of upper respiratory tract infections, lower respiratory tract infections, skin and soft tissue infections, alimentary tract infections, other viral infections, and miscellaneous infections with each tabulated by MedDRA PT.

8.2.3.2. Infusion-Related Reactions

Infusion-related reactions, defined as AEs that are identified as infusion related reaction by the investigator on the Infusion-Related Reaction CRF, will be summarized in a table and listing. The summaries will include the treatment group, dose level, cycle number, study day, date of

onset of AE, date of the associated infusion, and signs and symptoms of the infusion-related reaction.

